prescription and non-prescription medications used in pregnancy and the postpartum period. A urine drug screen will also be obtained at each visit testing for the presence or absence of the following: amphetamines/methamphetamines, barbiturates, benzodiazepines, THC, cocaine, methadone, opiates, PCP, and cotinine. For all visits following entry visit, subjects will complete the Patients' Global Impression of Change scale (PGIC) (Hurst and Bolton 2004); and the clinician will complete the Clinical Global Impression-Global Improvement scale (CGI-I) (Guy 1976). At all study visits, weight and vital signs will be collected. For all subjects who delivered at UAMS, medical records for labor and delivery and neonatal outcome will be obtained following birth. All subjects will participate in Part A. All subjects will receive treatment as usual within each group.

Part B:

Subjects in group 1 will be invited to participate in part B of the study following their enrollment in part A. This pilot study will aim to enroll 10 subjects (of Group A).

Subjects will undergo daily rTMS, defined as Monday through Friday, for a total of 10 consecutive sessions with the exception of weekends and holidays (i.e., Monday to Friday only). Typically, a stimulation period will start on Monday (day 1) and end on Friday (day 12). In the case that a stimulation period does not start on Monday, day 1 will begin on the day of the subject's first rTMS session. Subjects will be followed daily until day 29, following their last session of rTMS (day 12). Table 2 provides an overview of study procedures. For each session (days 1-5 and 8-12), subjects will complete a VAS prior, immediately following, and 60 minutes post. Adverse events will also be recorded prior to and immediately following and 60 minutes after each session. They will complete a BDI on Days 1, 5, 12, 22, and 29. Subjects will complete VAS also on days 22 and 29. For days 5, 12, 22, and 29; subjects will complete the PGIC; and clinicians will complete the CGI-I. Subjects will have a maximum of 12 visits for Part B (10 rTMS sessions plus days 22 and 29). Either study visit for days 22 or 29 may occur in conjunction with a study visit for Part A.

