An rTMS session consists of 10 trains at 90% intensity of resting motor threshold. One train consists of 50 pulses at 5 Hz for a 10s duration. There is a 50s intertrain interval. A total of 500 pulses are applied in a session for a cumulative exposure of 5000 pulses over 10 sessions. Each session lasts about one hour.

All rTMS treatments will be administered by the PI ([name]) or study staff who have been adequately trained to perform rTMS. [name] will receive training for rTMS through the intensive course in TMS offered by the Berenson-Allen Center for Noninvasive Brain Stimulation at Beth Israel Deaconess Medical Center – a teaching facility of Harvard Medical Center and device specific training from the device manufacturer, Neuronetics, Inc. Device specific training from the device manufacturer, Neuronetics, Inc., will also be provided for study staff. If potential adverse events occur during the treatments, the PI will follow the data and safety monitoring plan, as stated below. All participants will receive prompt medical treatment. As treatments are completed in an outpatient setting, emergency services will be utilized in the event of a series adverse event prompting emergency medical treatment.

Table 1: Data Information for All Study Participation (Part A)

MEASURES	ENTRY (≤24 weeks gestation)	PREGNANCY VISITS (EVERY 4-6 WEEKS)	POSTPARTUM VISITS (weeks postpartum)		
			0-4	5-8	9-12
SELF-REPORT MEASURES					
PDQ	X				
General Biographical Form (WMHP Intake Form)	X				
PCS	X	X	X	X	X
Pain Interference-Short Form 4A	X	X	X	X	X
Pain Behavior-Short Form 7A	X	X	X	X	X
Pain Intensity-Short Form 3A	X	X	X	X	X
VAS	X	X	X	X	X
BDI	X	X	X	X	X
PGIC		X	X	X	X
CLINICIAN-RATED MEASURES					
CGI-I		X	X	X	X
OTHER MEASURES					
Maternal Weight and Vital Signs	X	X	X	X	X
Exposure Tracking Form	X	X	X	X	X
OB/Delivery Records			X		
Neonatal Records			X		
Urine Drug Screen	X	X	X	X	X

Table 2: Data Information for rTMS Study Participation (Part B)

MEASURE	Days with rTMS			Day 1	Day 5	Day 12	Day 22	Day 29
	Pre	Immediately Post	60 mins Post					
VAS	X	X	X				X	X
Adverse Events		X	X					
BDI				X	X	X	X	X
PGIC					X	X	X	X
CGI-I					X	X	X	X
TASS	X							

Initial Screening

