Subjects will be identified by clinical staff based on current pregnancy status to identify potential subjects for the study. Once referred, initial screening by research personnel will include reviewing inclusion and exclusion criteria (as described in Eligibility Criteria) discussing the study, obtaining informed consent, completing the TASS questionnaire and initiating enrollment. These assessments and health related information will be collected on a paper form. All personnel will be qualified to administer all questionnaires.

Access to Medical Records: As a part of the informed consent for this protocol, individuals will allow the investigative team access to medical records. Any information acquired from medical records will be de-identified (no PHI, only subject ID code) and stored with the de-identified records obtained for this study.

The medical record will be utilized to gather obstetrical information regarding gestation and delivery of the infant, which may include but not limited to infant weight, height, APGAR scores, gender, head circumference, method of delivery and maternal or infant complications. Collection of health information will occur shortly following delivery of infant. Infants will only be assessed via medical records. There will be no direct assessment of infants within the scope of this study.

Questionnaires and Surveys for Parts A and B:

- Pain Interference Scale-Short Form 4a (Part A): This 4-item self-report scale measures the consequences of pain on relevant aspects of the subject's life. It includes impairment in the subject's social, cognitive, emotional, physical, and recreational activities. It also incorporates items about sleep and enjoyment of life. The short form is not disease specific and assesses pain interference over the past 7 days.
- Pain Behavior Scale-Short Form 7a (Part A): This 7-item, self-report scale measures behaviors that typically indicate to others that an individual is experiencing pain. These measures include observations (sighing, crying), behaviors (resting, guarding, facial expressions, asking for help), and verbal reports of pain. The short form is not disease specific and assesses pain interference over the past 7 days.

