
• Preterm labor• Preterm birth• Premature rupture of membranes• Mode of delivery	
• 1 minute and 5 minute APGAR Scores• Length of Hospitalization• Neonatal Intensive Care Unit Admission• Neonatal Abstinence Syndrome• Birth weight and length• Gender

Part B (rTMS):

We will determine the acceptability of rTMS as a treatment option by determining the percentage of subjects who accept the treatment when offered. Tolerability will be determined by the reporting of adverse events. The primary outcome measure is VAS. Secondary outcome measures include BDI, PGIC, and CGI-I. For each outcome measure, scatter plots will be constructed for visual inspection across treatment. Using previous studies of rTMS for the treatment of neuropathic pain, we will determine an effect size and complete a power analysis. This information will help guide future studies of the effectiveness of rTMS in the treatment of neuropathic pain in pregnancy.

Neonatal outcomes will be analyzed between the following groups: 1. Subjects participating in rTMS (Part B); 2. Subjects with neuropathic pain who participated in Part A but did not participate in Part B; 3. Subjects with chronic non-neuropathic pain who participated in Part A; and 4. Subjects without chronic pain who participated in Part A. Specific endpoints of interest include neonatal intensive care unit admission, length of hospitalization, birth weight and length, and 1-min and 5-min APGAR scores. The occurrence of obstetrical outcomes will be compared between the groups. If measures are normally distributed, we will use ANOVA to test the differences among the three groups. Otherwise, we will use a non-parametric method, such as Kruskal Wallis test, to test the difference among the groups.

Neonatal outcomes will be scrutinized after each delivery and neonatal period. The investigator team will convene and review all neonatal outcomes to determine if any complication occurred that could be attributed to the study, participation in the study, and/or treatment received. If any complication is identified (i.e. preterm delivery with all subjects who participated in rTMS), we will cease all current and potential study procedures related to part B of the study.

All statistical analysis will be completed using SAS 9.4. Significance will be set at $p<0.05$.

Data Safety and Monitoring Plan

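### Birth and neonatal records are provided for when delivery is at UAMS, but the outcome comparison and the neonatal review cover every birth, and no route to other hospitals' records is stated

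*Protocol*

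**What the plan says.** Under Investigational Plan, Part A, the protocol states: "For all subjects who delivered at UAMS, medical records for labor and delivery and neonatal outcome will be obtained following birth". It is the only sentence on retrieving birth records that names a place of delivery.

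Other parts of the plan deal with the same data without a site condition:

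- **Access to Medical Records (under Initial Screening).** As part of consent, "individuals will allow the investigative team access to medical records". Then: "The medical record will be utilized to gather obstetrical information regarding gestation and delivery of the infant", and "Collection of health information will occur shortly following delivery of infant". No hospital is named.
- **Table 1.** Its title covers all Part A participation. It marks obstetric/delivery records and neonatal records at 0-4 weeks postpartum.
- **Objective II.** Obstetrical and neonatal outcomes are compared across the three pain groups, not across UAMS births.
- **Statistical Methods, Part B, and the same text in the SAP.** "Neonatal outcomes will be scrutinized after each delivery and neonatal period". The investigators review all neonatal outcomes and stop Part B if a complication is identified. The endpoints are listed: "Specific endpoints of interest include neonatal intensive care unit admission, length of hospitalization, birth weight and length, and 1-min and 5-min APGAR scores".

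The medical-records paragraph also fixes the source of infant data: "Infants will only be assessed via medical records". The Eligibility Criteria for Parts A and B do not require a planned UAMS delivery.

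**The concern.** Staff working from the Part A sentence would collect records for UAMS births. Staff working from Table 1 or the medical-records paragraph would try to collect them for every birth. The plan does not say which governs, and nowhere describes how to obtain records of a birth at another hospital.

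The restriction matters because infants have no other planned source of data. If it is applied, an infant born elsewhere has no Apgar score, birth weight, birth length or exact length of stay. Two uses of the data are then exposed. The Objective II comparison would run on births selected by where they took place. The neonatal review in Part B, which can stop rTMS, would run on an incomplete set of exposed infants. Place of birth may be related to outcome in either direction, so the analysis could not reliably correct for the selection afterwards. The SAP says nothing about births without records, so a reader of the results could not see how many were missing.

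**Working it through.** The plan gives no figure to reproduce, so the main check is of wording; the arithmetic below only shows scale.

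**1. Does the site limit appear elsewhere?** No. Table 1, the medical-records paragraph, Objective II, Table 3 and the Part B neonatal review all omit it, in the protocol and, where repeated, in the SAP.

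**2. Can births occur elsewhere?** Yes. UAMS delivery is not an eligibility criterion. The qualifier in the Part A sentence would also have no purpose if every birth were at UAMS.

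**3. Which endpoints depend only on the record?**

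- Apgar scores, birth weight and length, and exact length of stay: no other stated source.
- NICU admission: might surface another way. Postpartum visits fall at 0-4, 5-8 and 9-12 weeks (Table 1), adverse events are assessed at each visit, hospitalization is a seriousness criterion, and infants are counted as enrolled.
- Preterm delivery: might surface from the delivery date, which is needed to place the postpartum visits.
- Neither of these last two routes is set up to collect the endpoint for every birth. The intake form has a section on the current or most recent pregnancy and may be updated, but its items are not shown.

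**4. Scale under an assumed off-site share f.** Inputs from Subject Selection: 60 mothers and up to 70 infants in Part A; 10 mothers in Part B. The share f is an assumption.

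Mothers without records = 60f. Infants = 70f at the planned maximum. rTMS mothers = 10f. Chance that at least one rTMS delivery lacks records = 1 − (1 − f)^10, taking deliveries as independent and f as the same in rTMS women.

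| f | Mothers (of 60) | Infants (of 70) | rTMS mothers (of 10) | Chance of at least one rTMS gap |
|---|---|---|---|---|
| 0% | 0 | 0 | 0 | 0% |
| 5% | 3 | 3.5 | 0.5 | 1 − 0.599 = 40% |
| 10% | 6 | 7 | 1 | 1 − 0.349 = 65% |
| 20% | 12 | 14 | 2 | 1 − 0.107 = 89% |
| 30% | 18 | 21 | 3 | 1 − 0.028 = 97% |

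**5. What missing records do to a rate.** For a yes/no endpoint known only from records, with x events seen among the n(1 − f) women with records in a group of n, the full-group rate lies between x/n and (x + nf)/n. The width is f by construction. Example with n = 20 and x = 2 (both assumed): at f = 5%, observed 2/19 = 10.5%, bounds 2/20 = 10% to 3/20 = 15%. At f = 20%, observed 2/16 = 12.5%, bounds 10% to 6/20 = 30%.

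**The case against.** The strongest reply is that nothing here is a contradiction. Table 1 is offered as an overview and need not repeat conditions, the medical-records paragraph describes permission and content, and the Part A sentence is the specific rule: a feasibility limit in a single-centre pilot. Alternatively, that sentence never says that records are sought only for UAMS births. It may describe the routine in-house route, with general consent covering the rest. Either reading is possible, and that is what stands: a reader might infer that the plan forbids collecting outside records, and the documents do not go that far. But if the limit is deliberate, Objective II and the review of all neonatal outcomes need the same limit. If it is not, the sentence should go.

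Second, every woman gives consent and HIPAA authorization, consent pages are not part of the material reviewed, and standard operating procedures are mentioned but not shown. A reader might infer that the study has no authority to request outside records. That cannot be judged from the documents.

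Third, a reader might infer that the Part B review would be blind to harm in off-site births. That is too strong, since NICU admission and preterm delivery could come to light at the postpartum visits. What stands is that this depends on chance reporting.

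Fourth, recruitment is entirely at UAMS sites, including its obstetric clinic and units, so the off-site share may be very small. This stands in full: no size can be set from the documents.

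Fifth, this is a small pilot with no stated power, and a few missing records may not change what it can conclude. That limits the weight of the point, but with a planned 10 rTMS mothers each infant record counts in the safety review.

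**Conclusion.** The point holds in a limited form. It is clear from the text that the Part A provision covers UAMS births while the uses of the data cover all births, and that no route to other records is stated. Whether data would be lost depends on which text staff follow, on procedures not shown, and on how many women deliver elsewhere; confidence that data would be lost is medium.

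If the provision is followed as written, Apgar scores, birth weight and length, and exact length of stay are lost for off-site births, while NICU admission and preterm delivery are captured only incidentally. Objective II and the neonatal review then rest on births selected by place of delivery. The direction of any bias is unknown and its size cannot be given. The 40% chance of at least one gap among 10 rTMS deliveries is an illustration at an assumed 5% share, with independent deliveries; it falls to zero as the share does.

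**What to change.** - **Protocol, Investigational Plan, Part A:** delete the clause that restricts record retrieval to UAMS births. State that labor, delivery and neonatal records will be requested from whichever hospital delivered.
- **Consent and HIPAA authorization:** confirm that the existing forms cover outside hospitals for mother and infant. Amend them only if they do not.
- **SAP:** for each comparison group, including rTMS, report the number of births with and without records.

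If the sponsor does want UAMS births only, the same limit should be written into Objective II, Table 1 and the neonatal review, with the same counts reported. This is the weaker choice, because it keeps the selection by place of birth.

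Cost: the wording change needs IRB approval before use (Independent Study Monitoring), and women already enrolled may have to sign a new authorization if the current one falls short. Outside requests, counting up to 60 + 70 = 130 record sets in all, come to 130f: 6.5 at an assumed 5% and 39 at 30% over the whole study, and fewer if the share is lower. Some outside hospitals will be slow or will not reply, so a few records may stay missing; the counts by group would show this. No new visits or study procedures are needed.

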Maternal Exclusion Criteria

- Active or history of substance use disorder within the past year
- Non-English speaking

Part B:

Maternal Inclusion Criteria

- Subjects enrolled in Part A and willing to consent to Part B of this protocol
- Pregnant with current chronic neuropathic pain
- Subjects failed treatment with amitriptyline or nortriptyline as defined by one of the following:
 - no clinical improvement following a four week trial of amitriptyline or nortriptyline (i.e., CGI-I score ≥ 4)
 - an inability to tolerate the medication (i.e., side effects)
- Subjects must pass the TMS Safety Checklist Adult Safety Screen (TASS).
- Subjects should be off medication, which can lower seizure thresholds (e.g., amitriptyline and nortriptyline) for at least two weeks prior to study entry.
- Subjects with neuropathic pain including those with diagnosis of spinal cord injury, fibromyalgia, compression neuropathies (including diabetic peripheral neuropathy), post stroke pain, and multiple sclerosis
- Subjects with a baseline VAS score greater than 30

Protocol Title: Neuropathic Pain in Pregnancy
Institution: University of Arkansas for Medical Sciences (UAMS)
IRB Number: 204737
Sponsor: UAMS
PI: [name]

Maternal Exclusion Criteria

- Current or past history of a seizure disorder (e.g., epilepsy)
- Current history of preeclampsia
- Current or history of brain lesions (e.g., aneurysm)
- History of major head trauma (e.g., stroke; previous cranial neurosurgery)
- Ferromagnetic metal in the head, neck, or chest (e.g., plates or pins, bullets, shrapnel)
- Microprocessor implants in the head (e.g., cochlear implants) or life-sustaining microprocessor implants anywhere in the body (e.g., prosthetic cardiac valves)
- Cardiac pacemaker
- Active or inactive implants (e.g., deep brain stimulators, vagus nerve stimulators)
- Active treatment with medications that lower seizure threshold (e.g., bupropion, amitriptyline, nortriptyline, or other TCA)
- Increased intracranial pressure (which lowers seizure threshold)
- Implanted medication pumps
- Intracardiac lines
- Significant heart disease defined as heart disease that causes moderate to severe symptoms and/or is characterized by moderate to severe pathology, including a recent history of myocardial infarction and heart failure with an ejection fraction of less than 30% or with a New York Heart Association Functional Classification of Class III or IV.
- Bipolar disorder (to reduce the risk of mania)

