- Beck Depression Inventory (BDI) (Part A and B): The BDI is a widely used instrument that has been used in both clinical and non-clinical setting measuring depressive symptoms. It is a 21 item questionnaire with 4-5 responses for each question. Responses are coded 0-3 for the 4 point scales. The 5 point scales include an additional 2a and 2b response code. The symptom categories reflect overt behavioral manifestations of depression. The instrument has both a high degree of reliability and validity (Beck, Ward, Mendelson, Mock & Erbaugh, 1961). This scale will be performed at every subject visit.
- Patient's Global Impression of Change Scale (PGIC) (Part A and B): The PGIC gives a global rating of change in symptoms, activities, emotion, and overall quality of life related to the subject's pain condition. This is a self-rated scale.
- Clinical Global Impression-Global Improvement Scale (CGI-I) (Part A and B): The CGI-I gives a global rating of the improvement/change in the symptoms since the last study visit. This is administered by the MD.
- Visual Analog Scale (Part A and B): 100 mm line scale that is subject administered to subjectively rate current pain symptoms. The subject will be instructed to draw a single vertical line that best describes current state. The VAS will be administered at every subject visit.
- TASS: TASS is the Transcranial magnetic stimulation Adult Safety Screen that is used to alert investigators to factors in potential subjects that may be predisposed to adverse events during rTMS. The decision to proceed with rTMS is entirely up to the investigator's judgment. TASS complements history-taking and is not meant to exclude or replace the investigator's judgment.

Maternal Labs

We will obtain maternal urine collection for research analysis at every subject visit for urine drug screen and cotinine analysis. Urine will be collected and processed in a designated research space at PRI/UWC or in the subject's room in PRI/UAMS and will be sent to an outside laboratory. WMHP research personnel process the research lab. All research samples will be temporarily stored in a dedicated -20 degrees freezers in the Psychiatric Research Institute (PRI) 4th floor laboratory. Access to the samples will be restricted to WMHP research personnel.

Cotinine/Nicotine

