All data will be kept either in locked file cabinets or password-protected computers accessible to only investigators or designated study staff. Trained study staff will enter data and original source documents will be stored in locked file cabinets in offices with limited access. A database will also be created to input subject information and only designated study staff will have access. Periodic reviews will occur to ensure that data is accurately entered and if needed, corrections can be made. The database will generate queries to account for missing information. Every subject enrolled in this study will be given a unique ID number that will be used for tracking purposes. The key linking the unique study ID number to identifiable information will also be stored in the password-protected computers accessible to only investigators or designated study staff. Each subject's name, SSN, birth date, address, phone number, and email address will be obtained for purposes of payment and follow-up. We will ask for each subject's drug use history, medical history, and current drug use.

Part A:

Descriptive statistics will be calculated for all measures obtained.

For the first hypothesis, primary outcome measures include VAS and pain assessments. Secondary outcome measures include BDI, PGIC, and CGI-I. For each outcome measure, scatter plots will be constructed for visual inspection across time by group. As outcome measures will be obtained at multiple time points, mixed models will be used to account for the correlations among the measurements within the subjects.

Table 3 provides a list of specific outcome data of interest for the second hypothesis. The occurrence of obstetrical outcomes will be compared between the three groups. If measures are normally distributed, we will use ANOVA to test the differences among the three groups. Otherwise, we will use a non-parametric method, such as Kruskal Wallis test, to test the difference among the groups.

Protocol Title: Neuropathic Pain in Pregnancy
Institution: University of Arkansas for Medical Sciences (UAMS)
IRB Number: 204737
Sponsor: UAMS
PI: [name]

Table 3: Specific Outcome Data

Obstetrical Records	Neonatal Records

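### The Part A analysis of the Group 1 pain course and analgesic use does not separate women who go on to rTMS in Part B

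*Protocol*

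**What the plan says.** **Objective.** Objective I (Protocol, Objectives) is to describe the course and drug management of neuropathic pain through pregnancy and postpartum, including analgesic use. It does not say whether this means the course under usual care or under whatever treatment is received.

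**Groups and follow-up.** Three groups are formed from the painDETECT score at entry. Table 1 shows that the questionnaire is not repeated. Part A visits run every 4-6 weeks to about 3 months postpartum. The Part A text ends: "All subjects will participate in Part A. All subjects will receive treatment as usual within each group".

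**rTMS pilot.** The pilot recruits from women already in the cohort: "Subjects in group 1 will be invited to participate in part B of the study following their enrollment in part A". The aim is 10 women, each with 10 rTMS sessions ending on about day 12. On combined visits the Protocol adds: "Either study visit for days 22 or 29 may occur in conjunction with a study visit for Part A". On medication, the inclusion criteria state: "Subjects should be off medication, which can lower seizure thresholds (e.g., amitriptyline and nortriptyline) for at least two weeks prior to study entry". The exclusion criteria also bar current use of such drugs.

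**Analysis.** For Part A (same text in Protocol and SAP), VAS and the pain assessments are primary, and BDI, PGIC and CGI-I secondary. For each, "scatter plots will be constructed for visual inspection across time by group", and mixed models handle repeated measures. No covariates, contrasts or rules for rTMS are listed. In the Part B section, the neonatal comparison does separate rTMS women from neuropathic-pain women who stayed in Part A only. It lists four groups, but the test sentence that follows refers to three.

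**The concern.** A Part B woman contributes Part A readings both before and after rTMS, all labelled Group 1. A plot or model by entry group therefore averages treated and untreated women at the later visits. If Objective I is read as the natural or usual-care course, a late fall in Group 1 pain could be usual care, rTMS or both, and the planned Part A display could not tell the reader which.

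The analgesic-use summary has a similar problem. Part B entry restricts drugs that lower seizure threshold and names two tricyclics. A medication change linked to Part B entry can therefore fall before the first session and still be counted as Group 1 management.

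The plan already treats Part B status as worth separating for neonatal outcomes. It does not do so for pain, which is the Part A primary outcome.

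**Working it through.** The documents give no SD, rTMS effect, Group 1 size or power figure, so there is no design figure to reproduce. The check is whether post-rTMS data enter the Group 1 series and, if so, by how much they could move it.

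**1. Do post-rTMS readings enter Part A?** Yes. Group is fixed at entry, and Part A visits continue to about 3 months postpartum. Days 22 and 29 come 22 − 12 = 10 and 29 − 12 = 17 days after the last session, and either may double as a Part A visit. The share depends on timing. Example (assumed): entry at 12 weeks, first session at 18, visits every 6 weeks, delivery at 40, three postpartum visits.
- Part A visits: weeks 12, 18, 24, 30 and 36, plus 3 postpartum = 8.
- After the first session: weeks 24, 30 and 36, plus 3 = 6, so 6/8 = 75%.
- With assumed entry at 8-24 weeks, first session 2-6 weeks later and 4-6 week visits, the share is about 67-92% of a treated woman's Part A visits.

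**2. Shift in the Group 1 mean at a post-rTMS visit.** Let n be the Group 1 size, m the number treated by that visit, d the mean rTMS effect remaining at that visit and μ the mean without rTMS.

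Group 1 mean = [(n − m)μ + m(μ − d)]/n = μ − (m/n)d, so the shift is (m/n) × d.

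With m = 10 (the enrolment aim); n and d are assumed:

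| n | m/n | d = 0 | d = 5 mm | d = 10 mm | d = 20 mm |
|---|---|---|---|---|---|
| 20 | 0.50 | 0 | 2.5 | 5.0 | 10.0 |
| 30 | 0.33 | 0 | 1.7 | 3.3 | 6.7 |
| 40 | 0.25 | 0 | 1.25 | 2.5 | 5.0 |

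n = 20 is one third of the 60 planned. If only 5 of 20 are treated, d = 10 gives (5/20) × 10 = 2.5 mm. If starts are staggered or the effect fades, m or d at a given visit is smaller and the shift falls in proportion.

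**3. What can a split by Part B status show?** The 95% half-width for Part B minus other Group 1 women at one visit is t × SD × √(1/10 + 1/(n − 10)), with an assumed VAS SD of 20-25 mm.
- n = 20: 2.10 × 20 × √0.20 = 18.8 mm; with SD 25, 23.5 mm.
- n = 30: 2.05 × 20 × √0.15 = 15.9 mm; with SD 25, 19.8 mm.

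These are far wider than the shifts in step 2, so the split can only be descriptive.

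**4. What does censoring cost?** For a simple mean at one late visit with n = 20, SD 20 and all 10 treated women censored, the standard error rises from 20/√20 = 4.5 mm to 20/√10 = 6.3 mm. A mixed model recovers part of this from earlier visits, but the estimate remains less precise.

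**The case against.** Several stronger readings are tempting, and the documents do not carry them.

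- **That the SAP orders pooling.** It does not; it is silent. Pooling is what a plot and model by entry group produce when no rule for rTMS is given.
- **That the usual-care sentence flatly contradicts Part B.** It closes the Part A text, just before Part B begins. Part B has its own consent and its own objective. The sentence can fairly be read as saying that Part A changes nobody's care. It still says all subjects, with no exception, so it needs reconciling, but that is a point of wording.
- **That pooling is wrong.** It is wrong only if Objective I means usual care. If it means the course under any treatment received, the all-data model is the right one.
- **That the rTMS response would go unseen.** Part B has its own plots of VAS, BDI, PGIC and CGI-I across treatment, and exposures are recorded weekly. What is missing is the separation within the Part A course.
- **That Part B causes the medication changes.** Entry requires prior failure or intolerance of a tricyclic, and stopping such a drug could equally be usual care. A link is possible, not shown.
- **That CGI-I is distorted by shorter recall.** The Protocol says "The CGI-I gives a global rating of the improvement/change in the symptoms since the last study visit". A shorter interval arises only if Part B visits count as study visits and the optional combined visit is used. The postpartum windows already allow unequal gaps in all women, so the point does not rest on this.

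The objection to a censored model also has force. It discards data, and if rTMS has no effect or only a brief one, it loses precision for little or no gain in bias. That is a reason to make it supportive, not to omit it.

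**Conclusion.** The point holds as a gap in the Part A analysis, worth fixing at low cost. As written, the late Group 1 pain course and analgesic-use summary would combine usual care with rTMS, with nothing in the Part A output to show it.

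The size cannot be established from the documents. It is the treated share times the rTMS effect remaining at that visit: zero with no effect, and 2.5-5 mm for an assumed 10 mm effect with 10 treated of 40 down to 20. These figures assume that all 10 places fill and that every treated woman is past rTMS with the effect still present. A reader should not take them as an estimate of bias in this trial. The medication part does not need an rTMS effect, but whether Part B entry changes drug use beyond usual care is unknown.

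The mismatch between four listed groups and a test among three, in the Part B section of both documents, is a separate small error in the same handling of Part B status.

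**What to change.** 1. **Descriptive display.** Show the Group 1 course (pain measures, BDI, PGIC, CGI-I) and analgesic use by Part B status, with each treated woman's rTMS start marked. Do not test the split: status is set after entry, and Part B women are selected (VAS above 30, tricyclic failure, safety screen, consent).
2. **Supportive model.** Keep the all-data mixed model. Add one run that censors Part B women's Part A data at the first session. State that it is less precise, that it relies on a missing-data assumption, and that it does not remove selection into Part B or medication changes made before the first session.
3. **Target.** Say which of the two models answers Objective I: the course under any treatment received (all data) or under usual care (censored). Reconcile the usual-care sentence at the end of the Part A text with Part B.
4. **Group count.** In the Part B test sentence of the Protocol and SAP, replace the reference to three groups with the four listed. The three-group wording in the Part A section is consistent there and can stay.

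The cost is SAP wording, one extra plot and table, and one less precise supportive model. The first-session date is already available from Part B, and no new data or visits are needed.
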